9 PARTICIPANT PATHWAY FLOWCHART (STANDARD CONDITIONS)

9.1 PARTICIPANT PATHWAY FLOWCHART (COVID-19 CONTINGENCY)

10 DEFINITION OF END OF STUDY

The end of the study is defined as the final data collection for the last participant. This will be the final STAI Y-1 questionnaire completed 28 days after receipt of genetic test results and collection of user feedback.

11 STUDY DISCONTINUATION

The study may be stopped if the Sponsor or REC terminate it before the planned end date. The Sponsor and the Funder have the right to discontinue the study at any time for failure to meet recruitment goals, safety or other administrative reasons.

12 STATISTICS

We are seeking to evaluate whether digital delivery of pre-test information for BRCA-testing in breast cancer patients is non-inferior to current standard practice of 1:1 delivery from a healthcare professional regarding uptake of genetic test. Although the study is not primarily powered for these outcomes, data on measures relating to safety, effectiveness and clinician/patient acceptability will be collected.

12.1 Sample size and power calculation for measurement of study endpoints

Sample size

To ensure >95% likelihood of identifying ≥ 5 individuals with a pathogenic_variant at each of the two recruitment sites (prevalence in unselected breast cancer of BRCA pathogenic_variants is $\sim 2\text{-}3\%$) and to test thoroughly the respective pathway logistics as shown below:

- Digital pre-test information – genetic test – digital notification of results
- Digital pre-test information - genetic test – notification of results from genetic counsellor
- Pre-test information from genetic counsellor – genetic test – digital notification of results
- Pre-test information from genetic counsellor – genetic test – notification of results from genetic counsellor

Recruiting 500 cases per site would give 97% probability to detect ≥ 5 individuals with a pathogenic_variant per site (assuming, conservatively, the frequency of BRCA pathogenicity is 2%).

Power calculation for measurement of study endpoints

The table below illustrates the non-inferiority margin in the patient reported outcome measures we would predict on one-sided analysis for non-inferiority of BRCA-DIRECT against standard pathway.

| | Attrition | Predicted available participants (following attrition) | Assumptions (reference *) | Power | Sample size required for 80% power (digital: clinician = 1:1) | Significance level (one-sided) | Non-inferiority margin | Notes |
|----------------------|-----------|--|--------------------------------|-------------------------------|---|--------------------------------|------------------------|--|
| Test uptake | 0% | 1000 | 90% test uptake in both groups | 80-85% with 1000 participants | 934 | 0.025 | 5.5% | Calculated using http://www.hwasoon.kim/NISSC/#!/binary |
| STAI state T1 | 0% | 1000 | Mean 43.2, SD 13.5 (*58) | 90-95% with 1000 participants | 636 | 0.025 | 3 | Calculated using http://www.hwasoon.kim/NISSC/#!/continuous |
| STAI state T2 | 10% | 900 | Mean 43.2, SD 13.5 (*58) | 90-95% with 900 participants | 636 | 0.025 | 3 | |
| STAI state T3 | 20% | 800 | Mean 43.2, SD 13.5 (*58) | 85-90% with 800 participants | 636 | 0.025 | 3 | |
| Patient satisfaction | 20% | 800 | Mean 3.75, SD 1 (*59) | 90-95% with 800 participants | 56 | 0.025 | 0.75 | |
| Knowledge score T1 | 20% | 800 | Mean 5.71, SD 1.55 (*36) | >95% with 800 participants | 38 | 0.025 | 1.40 | |

12.2 Randomisation

12.2.1 Randomisation to pre-test information delivery

- Participants will be randomised equally between standard care and digital delivery of pre-test information.
- Randomisation will be stratified by site and will use random block sizes up to 12.

12.2.2 Randomisation to receipt of genetic test results via telephone appointment with a genetic counsellor (participants with normal genes)

- We estimate that 94-95% (940-950) participants will have a negative (normal) test result
- Randomisation lists, stratified by site, will be produced to randomly pre-select 2.5% of this cohort to receive their test results via a telephone appointment with a genetic counsellor.

Randomisation lists will be generated by the study statisticians using Sealed Envelope's randomisation list generator: <https://www.sealedenvelope.com/simple-randomiser/v1/lists>.

12.3 Internal pilot

When 120 participants have been enrolled (60 participants in each arm), recruitment will pause and study data will be reviewed as follows:

Recruitment:

Actual recruitment will be compared with predicted recruitment. Any potential barriers to recruitment will be identified through liaison with local sites and information collected on Study Summary Sheets completed by patients who were not interested in taking part in BRCA-DIRECT.

Retention:

Retention will be evaluated by reviewing:

- Participant initiated withdrawal
- Drop out as a result of non-completion of study tasks

Where participants have provided a reason why they wished to withdraw, these will be examined for any consistent themes. Drop out time point will be examined to search for any problems within the BRCA-DIRECT study pathway.

Compliance:

Timeliness of completion of study tasks throughout the participant pathway will be compared to expected timelines, to identify any non-random delays at study timepoints. Data from the Participant Satisfaction Survey and telephone interviews (user feedback) will be examined to assist with identifying the cause of any such delays.

Completion of the full pathway will be compared to expected compliance. If compliance is less than expected, reasons why will be identified and resolved, where possible.

Preliminary review of participant knowledge following receipt of pre-test information and consent for genetic test:

We aim to provide participants with a clinician independent means of receiving information about genetic testing for BRCA genes that is not inferior to current practice. Review of Knowledge questionnaire data, user feedback and consent for genetic testing in 120 participants will highlight any major differences between the study arms that may require further investigation and resolution before recruitment recommences.

Data completeness:

Individual questionnaires will contain checks to prevent incomplete data. Non- completion of questionnaires will be examined at each study timepoint to search for any problematic timepoints. Reasons for non-completion of questionnaires will be identified and resolved, where possible.

Knowledge questionnaire and Participant Satisfaction Survey:

Pooled data will be examined to search for any consistent themes that may require resolution before recruitment recommences.

These study specific questionnaires are unvalidated. We will examine the pooled data for quality, and any deviations or exceptions to confirm that they are collecting secondary endpoint data robustly.

Referral to Independent Expert Group:

Any problems identified will be discussed by the BRCA-DIRECT Management Committee (MC) and local sites, as required, to resolve any issues. The progress of the study, including the internal pilot data, will be referred to the Independent Steering Advisory Group, along with any major problems identified that could affect the scientific integrity or quality of the study, including major barriers to recruitment.

The Independent Steering Advisory Group may seek further expert advice regarding continuation of the study, if required.

12.4 Statistical analysis

During this study and its internal pilot on the first 60 women randomised to each arm, we shall monitor closely and evaluate time taken for data collection, processing and analysis.

The progress of participants through the trial will be shown in a CONSORT⁶⁰ flowchart. Summary statistics will be calculated by trial group at baseline and at each follow-up time point. Normally distributed variables will be described by their means and standard deviations, skewed continuous variables by their medians and interquartile ranges and categorical variables by frequencies and percentages. The primary analysis will be on the per protocol population but we will also perform an analysis of complete cases following intention to treat principles. Further, we may use multiple imputation methods for quantitative outcome measures such as STAI, Patient satisfaction and Knowledge scores.

Continuous outcomes will be analysed using linear mixed effects models with fixed effects for baseline measure of outcome, randomisation arm, centre and time point, with a random effect for participant. Binary outcomes will be analysed using mixed effects logistic regression models with the same set of fixed/random effects. Other baseline covariates considered a priori to be prognostic of outcome may be included in these models. We will report two-sided 95% confidence intervals for each outcome comparison between the arms, with the main focus on comparison of the lower 95% confidence limit and the margin for non-inferiority. A full statistical analysis plan will be written and signed off prior to data analysis. Analyses will be conducted in Stata version 17.0⁶¹ or higher.

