Participants

Women with a diagnosis of breast cancer or high-grade ductal carcinoma in situ, currently attending breast clinics at the Royal Marsden NHS Foundation Trust and Manchester University Hospitals NHS Foundation Trust, for management/follow up of their breast cancer.

Interventions

Current standard of care (500):

1:1 delivery via genetic counsellor of pre-test information and results for BRCA gene-testing (Standard of care is 1:1 delivery face-to-face, by telephone or by video-conference. In this study we shall use telephone only).

Intervention under test (500):

Digital delivery of pre-test information and results for BRCA gene-testing.

Primary Outcome

- Uptake of genetic testing (proportion of patients proceeding with BRCA-test following receipt of pre-test information)

Secondary Outcomes

- Knowledge about genetic testing for BRCA genes, following delivery of pre-test information
- Anxiety following delivery of pre-test information and test results

Additional secondary outcomes

- Study decline rates on account of lack of access to digital interface
- 'Test-offer-to-results' time (study compared to audit of timings under current pathways at participating centres)
- Helpline usage
- Healthcare professional satisfaction
- Patient satisfaction

Sample size

1000 participants

Internal Pilot

For the first 60 participants in each arm, pilot capture of outcome measures, including patient-reported, clinician and logistical outcome measures.

Study Duration

Two years total including development, set-up and shut-down

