7 MEASUREMENT OF STUDY ENDPOINTS

Uptake of genetic testing will be measured as the proportion of participants proceeding to genetic testing following delivery of pre-test information either digitally, or via a telephone consultation with a genetic counsellor.

Knowledge will be assessed using a study-specific questionnaire, designed to test knowledge in key areas of genetic susceptibility awareness for breast/ovarian cancer. The questionnaire has been (i) developed using two previously published questionnaires developed to evaluate knowledge following delivery of genetic counselling information about increased risk for breast cancer, (ii) tested on 3 clinical genetics professionals, 3 oncologists, and (iii) reviewed by our PPI panel comprising patients with breast cancer and patients who have undergone BRCA-testing^{40, 54}.

Anxiety will be measured using the Spielberger state-trait anxiety inventory⁵⁵ and the short form Intolerance of Uncertainty scale⁵⁶.

The Spielberger state-trait anxiety inventory consists of two self-administered, 20-item questionnaires, with each item rated on a four-point Likert scale. It assesses anxiety proneness (trait) and the current state of anxiety change (state). The Trait anxiety is measured only once and the State at each time point. High STAI scores signify greater anxiety.

Research suggests that intolerance of uncertainty may be very important in understanding worry and may play a key role in the etiology and maintenance of worry. Evidence for the connection between intolerance of uncertainty and worry comes from studies that established that worriers possess a number of characteristics that set them apart from non-worriers. For example, worriers have been

shown to require more information before arriving at a decision ⁵⁷. The need for additional information may be a means for lowering the level of uncertainty.

Decline on account of lack of access to digital interface will be assessed from completed anonymous study summary forms posted into the secure study hub drop boxes.

'Test-offer-to-results' time (study compared to audit of timings under current pathways at participating centres)

Helpline usage will be assessed from a central log of the number, content and duration of calls made to the genetic counsellor telephone hot line.

Healthcare professional satisfaction will be assessed using a study specific survey

Patient satisfaction will be measured using a digital study specific survey.

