8.3 Delivery of information about genetic testing for BRCA genes BRCA1, BRCA2, PALB2

Participants will be randomised 1:1 to:

(i) **Receiving digital information about genetic testing for BRCA genes via the BRCA-DIRECT study interface**

- Participants will be able to scroll forwards and backwards through the information visiting links etc.
- The BRCA-DIRECT study system will record participant activity to confirm that they have visited the information before proceeding to the next stage of the study.
- Participants will be able to call the telephone hotline with queries or if they would like further information.
- The final screen will provide a link to access the digital 'BRCA-test consent' form. Participants will be able to call the telephone hotline if they would like to be taken through the clauses on the form.

Or

(ii) **Receiving a current standard of care telephone consultation with a genetic counsellor**

- Participants will be instructed to book an appointment with a genetic counsellor via a digital calendar located on the BRCA-DIRECT interface. They will be asked to book an appointment within the next three working days, if possible.
- At the end of the consultation, the genetic counsellor will inform the participant that a digital 'BRCA-test consent' form is available to be completed and signed via the BRCA-DIRECT interface. An explanation of the individual clauses within the form will be given.
- The genetic counsellor will log the consultation as completed and enable the digital consent form.
- A standard summary of the consultation will be sent via post to the participant.

If a participant does not book a genetic counselling appointment or commence viewing the digital pre-test information, an SMS/email reminder will be sent 1, 2 and 3 days after notification of the randomised allocation was received.

If a participant is unavailable during the booked appointment time they will be invited to book another appointment three additional times by the BRCA-DIRECT study system.

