8.4 Consent to proceed to genetic testing

- For both arms, if a participant decides to proceed with the genetic test they will sign a digital 'BRCA-test consent' form, which will be formatted to BSGM (British Society of Genomic Medicine) standards. All participants will receive a copy of their signed BRCA-test consent form via secure email/post.
- The participant will have two days following test-consent to reverse the decision to proceed with the BRCA-test. Beyond those two days, the test will proceed.
- If a signed 'BRCA-test consent' form is not received from a participant, the BRCA-DIRECT study system will send three reminders 1, 2 and 3 days after the participant viewed the digital pre-test information or had a telephone consultation with a genetic counsellor.
- If signed consent is not received after 8 weeks, the temporarily stored sample and Expression of Interest form will be destroyed and the participant will be withdrawn from the study.
- If a participant subsequently decides to proceed to genetic testing during the active period of the study, and is willing to provide another saliva/blood sample, this will be discussed with the patient and a test conducted if feasible.

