8.12 Participant withdrawal

[figure not shown]
Participants may withdraw from the study at any time, if they so wish, without giving a reason. Information about withdrawal is included in the patient information leaflet, as well as on the BRCA-DIRECT platform. Participants can withdraw by contacting their clinical team, the study hotline or emailing [contact].

No further data will be collected about that individual. Study data collected up to that point will be retained for audit purposes. Samples derivatives (DNA) and data generated within the NHS diagnostic environment will be retained.

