16.2 Ethical considerations and informed consent

This study will be carried out in accordance with the declaration of Helsinki (1996).

In order to avoid the need for patients to make extra visits to clinic, potential participants who are interested in participating in BRCA-DIRECT may be required to provide an 'upfront' saliva/blood sample before they have taken at least 24 hours to read the patient information leaflet and sign a consent form. To enable temporary storage of their saliva/blood sample, potential participants will be asked to complete and sign an Expression of Interest form, listing their email/mobile phone

contact details and giving the local site permission to store their sample while they decide whether to participate in the study.

Potential participants will be provided with a patient information leaflet and a study consent form that can be completed at home and returned in a pre-paid envelope. A telephone hot line to the local site genetic counsellor will be available during weekday office hours for patients to call if they require more information or have any queries.

In order to issue automated reminders to potential participants, their email/mobile phone details supplied on the EOI will be temporarily held on the BRCA-DIRECT study databases.

Upon receipt of a signed study consent form, the local site will enter a participant's baseline data onto the study databases to activate their account but the BRCA-DIRECT platform will not contact the participant for a further 24 hours. A link to a withdrawal screen will be available to participants immediately upon participation, so that they can withdraw at baseline.

If a potential participant decides not to participate in the study, or a signed study consent form is not received, their saliva/blood sample and Expression of Interest form will be destroyed and their contact details removed from the study databases.

Participants will not be able to sign digital BRCA-test consent for their saliva/blood sample to be tested until the BRCA-DIRECT system has recorded receipt of pre-test information, via data entry that a genetic counselling appointment has taken place, or electronic confirmation that the digital pre-test information has been visited.

There will be a 48 hour pause following receipt of digital consent for genetic testing to proceed before the instruction to process a sample is generated.

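### The primary uptake analysis rests on an undefined per-protocol set, and nothing says how a randomised woman who never receives the pre-test information is counted

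*Combined protocol and SAP*

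**What the plan says.** On the analysis set, section 12.4 says: "The primary analysis will be on the per protocol population but we will also perform an analysis of complete cases following intention to treat principles". Neither set is defined there or elsewhere. A fuller analysis plan is promised before data analysis but is not part of these documents.

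On the endpoint, the Summary describes uptake as the "proportion of patients proceeding with BRCA-test following receipt of pre-test information", and section 7 as the "proportion of participants proceeding to genetic testing following delivery of pre-test information". Either can be read with all randomised women, or only informed women, as the denominator.

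On women who do not reach the information, section 8.3 provides three reminders for anyone who "does not book a genetic counselling appointment or commence viewing the digital pre-test information", and three further booking invitations after a missed call. It gives no end state after that. Section 16.2 blocks test consent "until the BRCA-DIRECT system has recorded receipt of pre-test information".

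On withdrawal, section 8.4 says that when test consent has not arrived after 8 weeks the stored sample and form are "destroyed and the participant will be withdrawn from the study". It also allows later testing: "If a participant subsequently decides to proceed to genetic testing during the active period of the study". Section 8.12 says of withdrawn women: "Study data collected up to that point will be retained for audit purposes". Neither section says whether such women are analysed as non-uptake, treated as missing or left out.

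On planning, the uptake row of the section 12.1 table assumes 90% uptake in both arms, 0% attrition, 1000 available participants, a one-sided level of 0.025 and a margin of 5.5 points.

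**The concern.** A woman who was informed and did not sign is plainly a non-uptake. The gap concerns the woman who was randomised but never informed. Receipt happens after randomisation and is reached differently in the two arms: opening a link and viewing text, or booking and keeping a call. Failure to get that far is one of the ways in which the two routes can differ in uptake.

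Since no receipt means no consent, a receipt-based set removes failures and never successes. If the arms lose different shares of women in this way, the comparison loses part of the effect that the primary objective asks about. For a non-inferiority claim the harmful direction is more non-receipt with digital delivery.

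The planned intention-to-treat analysis is not a sure safeguard. It is secondary and is described as complete-case, so a withdrawn woman could be treated as missing there too.

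**Working it through.** **Inputs.** From section 12.1: 90% uptake in both arms, margin 0.055, one-sided 0.025, 1000 women (500 per arm). The documents give no non-receipt rates, so those below are assumptions. The method is the unpooled normal approximation to a difference in proportions, which is simpler than the mixed logistic model planned in section 12.4.

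**1. The plan's own figure.**
- n per arm = 2p(1-p)(z₀.₉₇₅ + z₀.₈₀)²/margin² = 2 × 0.90 × 0.10 × 7.849/0.055² = 467.04, so 934 in total, as stated.
- With 500 per arm, SE = √(2 × 0.09/500) = 0.01897. Power = Φ(0.055/0.01897 - 1.960) = Φ(0.939) = 82.6%, inside the stated 80-85%.
- The sample-size figure is not in error.

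**2. Non-receipt 2% telephone, 5% digital; 90% uptake among receivers in both arms.**
- *Excluded:* 490 and 475 women, difference 0. SE = √(0.09/490 + 0.09/475) = 0.01932. Expected lower 95% limit = -1.96 × 0.01932 = **-3.8 points**, inside the margin.
- *Counted as no uptake:* telephone 0.98 × 0.90 = 0.882; digital 0.95 × 0.90 = 0.855; difference -2.7 points. SE = √(0.882 × 0.118/500 + 0.855 × 0.145/500) = 0.02136. Expected lower limit = -2.7 - 4.2 = **-6.9 points**, outside the margin.

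**3. Other patterns, same 90% among receivers.**

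| Non-receipt (telephone / digital) | Lower limit, excluded | Lower limit, counted |
|---|---|---|
| 2% / 5% | -3.8 | -6.9 |
| 5% / 5% | -1.96 × √(2 × 0.09/475) = -3.8 | -1.96 × √(2 × 0.855 × 0.145/500) = -4.4 |
| 5% / 2% | -3.8 | +2.7 - 4.2 = -1.5 |

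Only the first pattern puts the two sets on opposite sides of -5.5.

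**4. Error rate when all-randomised uptake is exactly at the margin (84.5% v 90%), telephone non-receipt 2%.**
- Counting all randomised women, non-inferiority is declared 2.5% of the time.
- With 3% digital non-receipt, receivers' uptake is 0.845/0.97 = 0.8711 (n = 485) against 0.90/0.98 = 0.9184 (n = 490), a difference of -4.7 points. Non-inferiority is declared among receivers about 5.9% of the time. With 6% digital non-receipt it is about 48%.
- With equal non-receipt of 2% or 5% it is 2.2% or 1.7%.

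**5. Cost in power of counting everyone.** If the 90% already refers to all randomised women, power at 1000 stays at 82.6%. If it refers to informed women, equal non-receipt of 2%, 5% or 10% gives uptake of 88.2%, 85.5% or 81.0% in both arms, and power Φ(0.055/√(2p(1-p)/500) - 1.960) = 76.9%, 69.5% or 60.1%.

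**The case against.** - **The exclusion rule is not in the documents.** A reader might infer that the primary analysis will drop women who were never informed, and so is biased towards non-inferiority. The text does not say so. The endpoint wording allows that set, and the supported defect is that the set is undefined. This stands.
- **Section 12.1 points the other way.** The uptake row has 0% attrition and 1000 available, which suggests that all randomised women were meant to be counted. That weakens the concern, but a planning row is not an analysis rule. The same table gives 0% attrition to state anxiety at T1, which section 8.5 collects only after test consent; at 90% uptake at most 0.90 × 1000 = 900 women could supply it.
- **A large excess of digital non-receipt is not shown to be likely.** Before allocation a woman has given a sample, signed study consent and been asked to complete digital questionnaires. The longer route to receipt is by telephone, although that arm also has re-invitations. A reader might take the 48% error rate as a forecast; it needs a four-point excess that nothing in the documents supports.
- **Uptake among informed women is a legitimate question, and per protocol beside intention to treat is recognised non-inferiority practice.** Both are true. But the usual case for per protocol as the stricter analysis fails where exclusion coincides with failure on the endpoint.
- **The later analysis plan can settle it.** It can, but section 12.4 already fixes per protocol as primary and requires sign-off only before analysis. By then the pilot review in section 12.3 will have looked at drop-out and at consent by arm.

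**Conclusion.** The gap is real and should be closed before any comparison by arm. The primary set is undefined, the uptake denominator is open, and a receipt-based reading would remove only non-uptakes. The choice can decide the result: -3.8 against -6.9 points around a margin of -5.5. That rests on assumed non-receipt of 2% and 5%, on 90% uptake among receivers in both arms, and on a receipt rule that the protocol permits but does not state. With equal non-receipt, or more in the telephone arm, the conclusion in these examples is unchanged.

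The documents do not support saying that the plan will exclude these women, that the trial is biased, or that its sample size is wrong. Confidence is moderate, because the promised analysis plan may yet supply the rule.

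**What to change.** In section 12.4, make the primary uptake analysis all randomised women as allocated. Count signed and unreversed BRCA-test consent, within one window common to both arms, as uptake. Count everyone else as no uptake, including women never informed and women withdrawn before signing, so that the complete-case restriction removes nobody for this outcome. State in advance how the later testing allowed by section 8.4 is counted. Say in sections 8.4 and 8.12 that the allocation and uptake status of withdrawn women are used in the analysis.

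Keep per protocol as a supporting analysis with a written definition, or require both analyses to show non-inferiority. Report uptake among informed women descriptively by arm, with the numbers not reached.

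In section 12.1, state whether the 90% refers to all randomised women. If it refers to informed women, restate power at 1000 as about 77%, 70% or 60% for assumed non-receipt of 2%, 5% or 10% in both arms.

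The change to the analysis is one of wording, since the system already records receipt and signing. The price is that observed uptake may be lower and, if the 90% was meant for informed women, that the trial has less power than stated.

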2.3 Secondary Objectives

- To assess knowledge about genetic testing for BRCA genes, following delivery of pre-test information, in the two allocated groups
- To assess anxiety following delivery of pre-test information, and test results, in the two allocated groups

This study will be conducted in compliance with the protocol, standard operating procedures, policies, local R&D management guidance, Good Clinical Practice including the Research Governance Framework 2005 (2nd edition) and other applicable regulatory requirements as amended from time to time.

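### The planned mixed model gives one STAI arm effect pooled over T1–T3, not the three non-inferiority comparisons that were powered, and the lower-limit rule leaves the sign of the STAI difference undefined

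*Combined protocol and SAP*

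**What the plan says.** Section 12.4 gives one model for all continuous outcomes: "Continuous outcomes will be analysed using linear mixed effects models with fixed effects for baseline measure of outcome, randomisation arm, centre and time point", plus a random effect for participant. No arm-by-time interaction or time-specific contrast is named. Summary statistics by arm at each time point are planned, but only as description. For inference, two-sided 95% intervals are promised for every outcome comparison, "with the main focus on comparison of the lower 95% confidence limit and the margin for non-inferiority". The order of subtraction and the sign of the margin are not given.

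The table in section 12.1 treats STAI state as three separate rows, each at one-sided 0.025 with margin 3:

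- T1: 1000 available, power 90–95%
- T2: "90-95% with 900 participants"
- T3: "85-90% with 800 participants"

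Section 2.3 lists as a secondary objective: "To assess anxiety following delivery of pre-test information, and test results, in the two allocated groups". Section 7 says "High STAI scores signify greater anxiety". A full SAP is to be signed off before analysis; its text is not part of the document.

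**The concern.** There are two gaps between what is planned and what the stated analysis can deliver.

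**Time.** The time-point term and the participant random effect show that one joint repeated-measures model is meant, not a separate fit per visit. Without an interaction it has one arm coefficient, a precision-weighted average over T1, T2 and T3. It cannot be set against the margin at each visit, and it cannot separate anxiety after information from anxiety after results. Knowledge has the same problem: it is measured at T1 and T3 but has a margin only at T1.

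A constant effect over time is doubtful here. The randomised contrast is the pre-test information, and T1 follows it most closely. Sections 5.2, 8.6 and 12.2.2 set the mode of result delivery by test result and a random 2.5% selection, without reference to arm. An effect concentrated at T1 is therefore plausible, and that is the pattern pooling hides.

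**Sign.** Higher is better for uptake, knowledge and satisfaction, and worse for STAI. Under any one order of subtraction, the lower limit cannot be the relevant limit for both kinds of outcome. For STAI the rule is right for telephone minus digital and wrong for digital minus telephone. The same data could be read as passing or failing.

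**Working it through.** **Inputs.** From section 12.1: SD 13.5, margin 3, one-sided 0.025, 1:1 allocation, N = 1000/900/800 at T1/T2/T3. Assumed, because the document does not give them: equal within-person correlation ρ of 0.3, 0.5 or 0.7 between any two visits including baseline, and monotone dropout (800 people with T1–T3, 100 with T1–T2, 100 with T1 only).

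**1. The plan's own figures.**

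n per arm = 2 × 13.5² × (1.960 + 0.842)² / 3² = 317.9, so 318 per arm and 636 in total, as stated.

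Power = Φ(3/SE − 1.96), with SE = 13.5 × √(4/N):

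| Visit | N | SE | Power | Stated |
|---|---|---|---|---|
| T1 | 1000 | 0.854 | 94.0% | 90–95% |
| T2 | 900 | 0.900 | 91.5% | 90–95% |
| T3 | 800 | 0.955 | 88.2% | 85–90% |

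The table is correct, but as three single-visit, two-sample comparisons.

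**2. What the stated model estimates.** Generalised least squares for a random-intercept model with main effects of time and arm. With baseline adjustment, the residual variance is 13.5²(1 − ρ²) and the covariance 13.5²(ρ − ρ²). The arm coefficient weights T1, T2 and T3 by about 0.38–0.39, 0.33 and 0.28–0.29. Its SE is 0.590, 0.569 and 0.489 for ρ = 0.3, 0.5 and 0.7.

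P(declare non-inferiority) = Φ((3 − expected estimate)/SE − 1.96), taking digital minus telephone with upper limit below +3:

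| True difference at T1, T2, T3 | Expected estimate (adjusted) | P, adjusted, ρ = 0.3/0.5/0.7 | P, unadjusted (range) |
|---|---|---|---|
| +3, 0, 0 | 1.148/1.163/1.174 | 0.881/0.898/0.962 | 0.64–0.82 |
| +3, +1.5, 0 | 1.643/1.655/1.664 | 0.633/0.657/0.780 | 0.39–0.55 |
| +3, +1.5, +1.5 | 2.074/2.081/2.087 | 0.348/0.365/0.464 | 0.21–0.30 |
| +3, +3, +3 | 3.000 | 0.025 | 0.025 |

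For example, first row, ρ = 0.3: (3 − 1.148)/0.590 − 1.96 = 1.18, and Φ(1.18) = 0.88. A T1-specific test would pass 2.5% of the time in every row. Simulation of the first row (2,000 trials per value of ρ) gave 0.881, 0.898 and 0.960.

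**3. With the interaction added.** Power at true difference 0, for T1/T2/T3:

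- Baseline-adjusted: 95.8/93.9/91.3% (ρ = 0.3), 98.2/97.2/95.7% (0.5), 99.8/99.7/99.4% (0.7).
- Unadjusted, ρ = 0.3: 94.0/91.7/88.9% (taking 0.940, 0.917 and 0.889).

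All lie within or above the stated ranges.

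**4. Sign, at T1 with SE 0.854 and a true increase of 3 under digital.**

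- Digital minus telephone, lower limit above −3: Φ(6/0.854 − 1.96) > 0.999.
- Telephone minus digital, lower limit above −3: Φ(−1.96) = 0.025.

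**The case against.** - **Section 12.4 is an outline and a full SAP is promised.** The model sentence reads like a template: uptake is measured once and has no baseline value, and satisfaction has no baseline, so the listed terms cannot be literal for every outcome. That is fair, and the SAP is the place for the repair. But the protocol already names a model and a rule, and no text in hand adds the interaction. Reading the promised intervals as one per row of the table does not help, because the stated model does not produce one per row.
- **STAI is secondary.** The stated non-inferiority objective concerns uptake, and section 12 says the study is not primarily powered for other outcomes. This stands and limits the severity. Even so, section 12.1 gives STAI a margin, an alpha level and power, and section 12 groups these outcomes with safety and acceptability.
- **The largest figures come from the most extreme pattern and an assumed correlation.** This also stands; hence the graded patterns, including the one with no inflation.
- **The direction of harm can be inferred.** Sections 7 and 12.1 together make it clear which way is worse, so the >99.9% figure is a worst-case reading, not a likely error. Accepted: on its own the sign would be a one-line clarification.
- **The power claim needs two qualifications.** First, if all three STAI comparisons had to succeed, joint power would be 79–85% unadjusted and 83–99% adjusted. Second, T1 is collected only after test consent, so with 90% uptake about 900 people would reach it. If 10% and 20% attrition then applied to those 900, power at ρ = 0.3 would be 91.5/88.8/85.5% unadjusted, with T2 just below its stated range. The plan's model adjusts for baseline, and that gives 93.8/91.4/88.3%, inside all three ranges.

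**Conclusion.** The concern holds and should be fixed. As written, the model has one arm coefficient and does not match the three STAI comparisons in section 12.1 or the two periods in section 2.3. That follows from the text and needs no assumption.

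The size depends on the true pattern and on the assumed correlation of 0.3–0.7. For a margin-sized increase at T1, the pooled test would pass 88–96% of the time if the effect then vanished, 63–78% if it halved at T2 and vanished at T3, and 35–46% if it halved and persisted (all baseline-adjusted). The target is 2.5%, and a constant effect keeps it there.

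The undefined sign is a real but smaller gap. The power table's STAI figures are correct. The missing interaction does not touch the primary outcome, which is measured once.

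**What to change.** In the SAP, before data are analysed:

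1. Add an arm-by-time interaction to the model for repeated continuous outcomes. Report the arm contrast for STAI at T1, T2 and T3 and for knowledge at T1, each against its margin in section 12.1. Estimate knowledge at T3 without a margin test, since none is given.
2. State whether the three STAI comparisons are read separately or must all succeed. If all must succeed, give the joint power.
3. State the direction for each outcome. For STAI: digital minus telephone, upper 95% limit below +3. For uptake, knowledge and satisfaction: digital minus telephone, lower 95% limit above minus the stated margin.

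If a single pooled STAI effect is what is wanted, say so, and replace the three table rows with power for that effect.

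The cost is one model term and a few lines of wording. Sample size does not change, and with baseline adjustment the time-specific power stays within or above the stated ranges.
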